## 8. Sources of Research Material:

- Subjects undergoing colonoscopy
- Electronic Medical Record
- Anesthesia Reports
- PHI including name, medical record number, contact information including demographic information including age, gender, race, birth date, weight, height, BMI and medical and surgical history, medication list, ASA classification.
- **Procedural sedation-related variables:** type of sedation agent used for procedural sedation, propofol dose, propofol infusion time, opioid use, any other combination agent for the procedural sedation during colonoscopy, Procedure time, premature termination of procedure.
- **Respiratory event-related variables;** Anesthesiologist intervention (intubation, airway repositioning, Chin lift); Type of airway used (oral airway, nasal airway, bag mask ventilation, suctioning), Laryngospasm or any other airway obstruction; pulse oximetry reading, the number and duration of apnea/hypoxia episodes.
- **Hemodynamic variables** such as baseline blood pressure
- **Postoperative Recovery:** Aldrete score in recovery, the time spend in PACU
- Unplanned hospital admission

- Stop Bang questionnaire for OSA screening

### **9. Recruitment Methods and Consenting Process:**

All patient recruitment will take place in the GI endoscopy suite. Subject will be identified by reviewing daily endoscopy schedule. A designated team of anesthesiologists and nurse anesthetists involved in the study will be responsible for screening, consenting and enrolling potential subjects. The patient's chart will be reviewed to determine eligibility with the use of a HIPAA waiver form. Information about the study will be given in a pressure-free, confidential private area in a face-to-face meeting and the voluntary nature of the research will be emphasized to the subjects.

The purpose of the study and risks and potential complications of the study will be explained. Adequate time will be given to read consent form to consider whether or not participate in the study. All questions will be answered before the patient is asked to sign the consent form. If the patient agrees to participate, then he or she will sign the consent form and HIPAA Authorization Form prior to any study procedures.

### **10. Potential Risks:**

This study has minimal risk. The anesthetic management in either group will not differ from the current standard of care.

#### **Risk for HFNC:**

There may be minimal risk for mucosal injury with HFNC. This risk is not higher than standard nasal cannula because HFNC systems deliver heated, humidified gas.

HFNC may produce distending pressure in the lung, similar to CPAP pressures. There may be potentially unpredictable pressures generated by HFNC which may be significant in pediatric but not adult obese population. Mild distending pressure may provide better patent airway in obese subjects. Flow rate of HFNC will be adjusted for maximum benefit to the subject (40-60 L/minutes).

**Psychological Stress:** Some of the questions related to the study may make the subject feel uncomfortable. Subjects may refuse to answer any of the questions, or take a break or stop participation in the study at any time.

**Loss of Confidentiality:** Any time information is collected; there is a potential risk of loss of confidentiality. Every effort will be made to keep your information confidential.

### **11. Subject Safety and Data Monitoring:**

Investigators will ensure patient safety throughout the procedure. This will include following all standards of care with regard to conducting a safe anesthetic in the endoscopy suite. All standard ASA monitors will be used, adequate O2 delivery will be ensured and the proper interventions by the providers will be carried out during significant desaturation episodes. Subjects will recover from the anesthetic in the endoscopy suite recovery room. All data will be collected by the EMR as per usual (EPIC).

### **12. Procedures to Maintain Confidentiality:**

All participants will be given an identification number such that identifiable, personal information will not be used. Every effort will be made to keep all data collection sheets confidential and any electronic data sets will be password protected and secure. Electronic documents will be de-identified according to information security policies. Paper documents will be shredded.

### **13. Potential Benefits:**

There is no benefit to subjects. Use of the Comfort Flo high flow nasal cannula may lead to a significant decrease in hypoxic events in morbidly obese, likely sleep apneic, patients undergoing deep sedation for colonoscopies. Information gained from this study will increase patient safety and decrease the morbidity and possibly, mortality, in this challenging patient population.

### **14. Biostatistics:**

The study is powered to detect a 50% reduction in the frequency of desaturation episodes in patients with HFNC compared to patients using a standard nasal cannula. Quadeer et al. (3) reported a 51% incidence rate for desaturation episodes below 90% in patients with standard nasal cannula. Thus to detect a difference of 25% with 80% power and a type 1 error rate of 0.05, the study would need a sample of 59 per group (total n = 118). Assuming a 10% loss of subjects, the total sample size to be enrolled is 130. An interim analysis will be performed at 50% of the enrolment. Based on the interim analysis results, study may be stopped for futility if there is no difference in interim analysis or for early termination for effectiveness if the observed difference at the time is large enough. Obrien-Flemming  $\alpha$ -spending function approach would be used to develop acceptance or rejection boundaries. Continuous data will be summarized using means and standard deviations and categorical data will be summarized using frequencies and percentages. The proportions of desaturation episodes below 90% in the two groups will be compared using a Z test or Fisher's exact test. Mean durations of desaturation episodes and mean numbers of interventions to treat hypoxic events in the two groups will be compared using Student's t-tests or Wilcoxon-Mann-Whitney tests. Frequencies of sedation-related adverse events will be compared using chi-square tests or Fisher's exact tests. Normality of the sample data will be assessed using normal quantile plots. Level of significance will be set at 0.05 and Bonferroni corrections will be made for all primary hypotheses tests.

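### Does the interim futility stop need a numeric bound, given that the O'Brien-Fleming alpha-spending function named in the plan does not supply one?

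*Combined protocol and SAP*

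**What the plan says.** Everything on this point is in section 14 (Biostatistics). The design is "to detect a difference of 25% with 80% power and a type 1 error rate of 0.05", with 59 per group (118 in all), and "the total sample size to be enrolled is 130". On timing: "An interim analysis will be performed at 50% of the enrolment". Two stops are then allowed. The first is that the "study may be stopped for futility if there is no difference in interim analysis". The second follows in the same sentence: "or for early termination for effectiveness if the observed difference at the time is large enough". The method is given in the next sentence, where an O'Brien-Fleming alpha "spending function approach would be used to develop acceptance or rejection boundaries". The primary comparison is described as follows: "The proportions of desaturation episodes below 90% in the two groups will be compared using a Z test or Fisher's exact test".

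No futility cut-off appears as a Z value, p value, conditional power or beta-spending function, and no power with a futility rule is given. Section 11 (Subject Safety and Data Monitoring) contains no interim rule.

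**The concern.** An alpha-spending function allocates type I error across looks. It says when the null may be rejected, and so gives a number to the effectiveness stop. It does not say when a trial is hopeless; that needs a second rule. The plan mentions acceptance boundaries alongside rejection boundaries, yet names only the method that gives the latter.

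What is at stake is power. A lack of difference can mean an observed difference of zero or in the wrong direction. In loose usage it can also mean a non-significant result. With about 30 evaluable patients per arm at the look, a trial that observed exactly its planned 25-point difference would have Z = 1.99, barely past 1.96. If non-significance were enough to stop, about half of the trials with the planned effect would end at the interim, many of which would have been positive at full size.

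**Working it through.** **Inputs, from section 14 unless noted.** Salter group 51%; difference 25 points, so 26% with HFNC; 80% power; alpha 0.05; 59 per group; one look at 50%. Allocation is 1:1 (section 4). Assumptions: two-sided testing, one primary comparison (so no further Bonferroni split), information fraction 0.50, normal approximation.

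**1. The plan's sample size.** With p̄ = (0.51 + 0.26)/2 = 0.385,

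n = [1.960 × √(2 × 0.385 × 0.615) + 0.842 × √(0.51 × 0.49 + 0.26 × 0.74)]² / 0.25² = 58.3, rounded up to 59.

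This matches the plan. One-sided testing gives 45.8 (46), so the stated 59 implies two-sided 0.05.

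**2. What the named method supplies.** O'Brien-Fleming-type spending with 0.025 per tail, at t = 0.5:

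2 × [1 − Φ(2.241/√0.5)] = 0.001525 per tail.

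- Interim bound: |Z| = 2.963, two-sided p = 0.0031.
- Final bound, from the bivariate normal with correlation √0.5: |Z| = 1.969, p = 0.0490.

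The effectiveness stop can therefore be computed from what the plan states. Two-sided spending also gives a harm bound at −2.963, but no inner futility bound.

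**3. Power under different readings.** The standard error at 59 per group is √(2 × 0.385 × 0.615/59) = 0.0896. The expected final Z is 0.25/0.0896 = 2.79, and the expected interim Z is 2.79 × √0.5 = 1.973. The chance that a planned-effect trial stops for futility at bound f is Φ(f − 1.973). Power is the chance of crossing 2.963 at the look, or of lying between f and 2.963 there and exceeding 1.969 at the end. The stop is assumed to be taken every time it is allowed.

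| Reading | f | Planned-effect trials stopped | Power |
|---|---|---|---|
| No futility stop | none | 0% | 79.5% |
| HFNC no better than Salter | 0 | 2.4% | 79.2% |
| Beta-spending, O'Brien-Fleming type | 0.497 | 7.0% | 77.9% |
| Two-sided p > 0.05 | 1.960 | 49.5% | 48.4% |
| Effectiveness bound not crossed | 2.963 | 83.9% | 16.1% |

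The beta-spending bound spends 2 × [1 − Φ(1.282/√0.5)] = 0.070 of the 0.20 at the look, so f = 1.973 − 1.476 = 0.497. The cost against no futility stop is 79.5 − 79.2 = 0.3 points for the literal reading and about 1.7 points (before rounding) for beta-spending.

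**4. Sensitivity.** An exact binomial calculation with looks at 30 and 59 per arm shows the same pattern: 80.5% with no stop, 80.2% at f = 0, 79.4% at f = 0.52 and 49.4% for p > 0.05. If nobody is lost, 65 of the 130 enrolled give 65/118 = 0.551 of the information. With an expected final Z of 2.819, power there is 80.3% with no stop, 80.1% at f = 0 and 79.2% at f = 0.52.

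**5. Type I error.** A futility stop can only remove rejections. Per tail, the 0.025 becomes 0.0247 at f = 0 and 0.0236 at f = 0.497.

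**The case for a change.** The strongest case for a change is that leaving the stop to discretion does not protect the trial when no threshold guides that discretion. The section names a Z test or Fisher's exact test at 0.05, so someone at the look might take non-significance as the test for futility. By Fisher's test, 59% of planned-effect trials would then stop (exact binomial). At Z = 1.96 the conditional power under the planned effect is still 87%. One sentence of wording would close the gap.

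It stands that the plan gives no number and that alpha-spending alone cannot give one. The large losses, however, come from readings that the text does not state. It speaks of there being no difference, without mentioning significance. An unadjusted 0.05 cut-off also fits poorly with a plan to develop O'Brien-Fleming bounds. Stopping whenever the effectiveness bound is missed contradicts the plan's two separate conditions, which leave a middle zone where the trial continues; on that reading no trial would ever reach 118. The stop is also worded as permitted rather than required, which is ordinary non-binding language, and the bounds are described as still to be developed.

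Added wording would mostly record the literal reading. Choosing between a bound at 0 and one near 0.5 is a trade-off: the first costs 0.3 points of power and stops about 50% of null trials early, while the second costs about 1.7 points and stops about 69%. Either is defensible.

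**Conclusion.** The futility threshold is not specified numerically, but no change to the plan follows. It is a gap that a trial statistician would fill sensibly when developing the bounds. Under either sensible reading power stays at about 78% to 79%, against 79.5% with no futility stop (up to about 80% by exact binomial). Type I error does not rise, and the effectiveness bounds and sample size are unaffected. The fall to about 48% requires both a p > 0.05 rule that the plan does not contain and a stop taken every time it is allowed. The figures assume two-sided 0.05 (inferred from the 59 per group), a single primary comparison, a look at 50% information, and true rates of 51% and 26%.

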All patients will receive a similar intravenous anesthetic with a propofol infusion titrated to a Richmond Agitation-Sedation Scale (RASS) score of 3-4. A lidocaine bolus of up to 100 mg can be used prior to the start of the propofol infusion for initial tolerance of the drug. Patient saturation is recorded every minute during the anesthetic on the electronic medical record and is available for review. The duration and frequency of all measurements at or below 90% will be recorded by the Electronic Medical Record (EMR). The anesthesia providers will be instructed to intervene only when the patient's saturation falls below 90%, by either manually performing a jaw thrust, placing a nasal or oral airway, bag mask ventilation, increasing the patients FiO2 or decreasing the rate/ pausing the propofol infusion or endotracheal intubation. They will be instructed to write a quick note at the time of intervention in the EMR describing their maneuver. Duration of the study will be the length of the procedure through discharge from the Postoperative Anesthesia Care Unit (PACU).

Our hypothesis is that the patients in the high flow nasal cannula group will experience a marked reduction in intraoperative desaturation events as compared to the Salter cannula group.

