#### **Outcome Measures:**

- Lowest recorded saturation
- The frequency of desaturation episodes (SpO2 <90%)
- Duration of desaturation episodes (SpO2 <90%)
- Number of apnea episodes
- Dose of propofol or other combination for sedation during colonoscopy
- Anesthesiologist intervention (intubation, airway repositioning, Chin lift)
- Type of airway used (oral airway, nasal airway, bag mask ventilation, suctioning)
- Premature termination of procedure
- Unplanned hospital admission

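### The interim stopping rules do not say what happens if desaturation is more frequent on HFNC; the look should be defined directionally and tied to a pause

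*Combined protocol and SAP*

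**What the plan says.** Section 14 (Biostatistics) states: "An interim analysis will be performed at 50% of the enrolment". It gives two reasons to stop: the "study may be stopped for futility if there is no difference in interim analysis or for early termination for effectiveness", the latter "if the observed difference at the time is large enough". The boundaries are to come from an O'Brien-Fleming method: a "spending function approach would be used to develop acceptance or rejection boundaries". No boundary value is given, nor whether the boundaries are one- or two-sided, nor where a result favouring Salter would fall.

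Section 11 (Subject Safety and Data Monitoring) deals with care of the individual patient: "the proper interventions by the providers will be carried out during significant desaturation episodes". It provides for no review of accumulating data by arm and no condition for pausing the trial.

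Section 3 sets the bedside instruction for all patients: "The anesthesia providers will be instructed to intervene only when the patient's saturation falls below 90" per cent. Bag mask ventilation and intubation are among the listed interventions. The outcome list includes early termination of the procedure and "Unplanned hospital admission". Section 14 compares sedation-related adverse events between arms but does not link them to the interim look.

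**The concern.** The primary outcome, SpO2 below 90% under deep sedation, is itself an adverse event. The interim look will compare the arms on it at half enrolment, yet the written rules name only an absent difference and a difference that shows effectiveness. A difference in the wrong direction has no stated consequence.

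Section 2 says that no prospective randomized study has compared these devices in this population, so the direction of effect is not established. If HFNC does worse, the remaining patients are protected at trial level only if the unstated boundary happens to be built in a way that catches it. The serious airway events, early terminations and admissions that the trial already records enter no rule.

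**Working it through.** **Inputs.** From Section 14: 51% desaturation on Salter, a 25-point reduction (so 26% on HFNC), 80% power, alpha 0.05, 59 per group, 130 enrolled, one look at half enrolment. From Section 4: 1:1 allocation. My assumptions: the endpoint is the proportion of patients with any desaturation; 30 evaluable per arm at the look (29 and 32 also tried); a pooled Z test; true HFNC rates of 66%, 71% and 76% as harm scenarios. The last rate mirrors the planned benefit. The documents give no HFNC rate above 51%. Negative Z means HFNC is worse.

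**1. The plan's own figure.** With mean rate 0.385,

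n = [1.960·√(2·0.385·0.615) + 0.842·√(0.51·0.49 + 0.26·0.74)]² / 0.25² = 58.3, so 59 per group.

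This matches. The same formula with one-sided alpha 0.05 gives 46, so the plan's number implies a two-sided test. Adding 10% gives 118 × 1.10 = 130, as stated.

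**2. Patients still to come.** 130 / 2 = 65, of whom 65 / 2, or 32 to 33, would receive HFNC.

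**3. O'Brien-Fleming-type bound at half information.** With 0.025 per side, the alpha spent is 2[1 − Φ(2.241/√0.5)] = 0.0015, so the interim bound is |Z| ≥ 2.963 and the final bound about 1.969.

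**4. What each bound needs, with 15/30 events on Salter.**
- 25/30 on HFNC: Z = −0.333/0.122 = −2.74, which does not cross −2.963.
- 26/30: Z = −0.367/0.120 = −3.05, which crosses; the excess is 36.7 points.
- 21/30: Z = −1.58, which does not cross −1.645.
- 22/30: Z = −0.233/0.126 = −1.86, which crosses; the excess is 23.3 points.

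**5. Chance that each rule acts at the look** (exact binomial enumeration, 30 per arm, Salter 51%):

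| True HFNC rate | Symmetric bound, Z ≤ −2.963 | Illustrative harm bound, Z ≤ −1.645 | Assumed futility stop, Z ≤ 0 |
|---|---|---|---|
| 66% | 3.4% | 30.5% | 91% |
| 71% | 8.0% | 46.3% | 96% |
| 76% | 16.6% | 63.7% | 99% |
| 51% (equal) | 0.1% | 4.6% | 55% |
| 26% (planned) | 0.0% | 0.01% | 2.9% |

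With 29 or 32 per arm, the 76% row becomes 15.1% or 18.5% for the symmetric bound and 64.3% or 67.3% for the harm bound.

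**6. Power under 51% v 26%** (2,000,000 simulated trials, 30 then 59 per arm, bounds 2.963 and 1.969): 80.5% with no stop against HFNC, 80.5% with the harm bound, 80.1% with the Z ≤ 0 futility stop.

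**The case against.** The strongest reply is that the plan already has a futility rule and a directional hypothesis. In a usual directional futility analysis, a reversed result is the clearest case for stopping: under the planned effect, conditional power is about 22% at Z = 0 and below 1% at Z = −1.645. Reading the rule as one that stops at equality but carries on when HFNC is worse is uncharitable. On the directional reading, futility would stop more harmful trials than the illustrative harm bound, as the table shows. This stands, and it limits the point. It does not remove it: Section 14 describes futility as the absence of a difference, its sample size implies a two-sided test, and it gives no acceptance boundary. A region centred on zero is therefore an open reading.

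It is also fair that Section 10 describes minimal risk, that HFNC is set to an inspired oxygen fraction stated to match Salter at 4 L/min, that each patient is monitored and treated at the bedside, and that the permissive wording leaves the investigators free to stop for safety. Bedside care, however, cannot show an excess across an arm, and freedom to stop is not a prespecified rule.

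Three stronger readings are not supported:
- A reader might infer that about 83% of trials with a 25-point harm would continue. That is 100% − 16.6%, and it holds only if futility cannot act on a reversed result, which the plan does not say.
- A reader might infer that the whole second half would enter the worse arm. Under 1:1 allocation about half would.
- A reader might infer that harm is expected. The documents give neither a mechanism nor a rate for it.

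**Conclusion.** The point holds as a cheap improvement. No written rule covers an interim result against HFNC, and whether such a result would stop the trial turns on an unstated choice. At assumed HFNC rates of 66% to 76%, that choice moves the chance of stopping from 3%–17% (two-sided region with a symmetric bound) to 91%–99% (directional futility at Z ≤ 0).

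These figures rest on the plan's 51% Salter rate, about 30 evaluable patients per arm and hypothetical HFNC rates. The Z ≤ 0 cut-off is also an assumption. They show how much the missing definition matters; they do not show that HFNC is likely to do worse or that the trial is unsafe as designed.

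**What to change.** **Section 14.** State the sidedness of the boundaries and define the existing look so that a result favouring Salter falls in a stop-or-pause region. Use a directional futility boundary, a separate non-binding harm bound on the primary endpoint (for example one-sided 0.05, Z ≤ −1.645), or both. At the same look, tabulate by arm bag mask ventilation, intubation, premature terminations and unplanned admissions.

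**Section 11.** State that crossing the bound pauses enrolment for review by the investigators. If they want an event-count trigger as well, they should fix its threshold in advance; its clinical content is theirs to set. No new committee is needed.

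**Cost.** A short amendment and one extra table from data already collected. With the harm bound, the chance of an unnecessary pause is about 5% if the arms are equal; an event-count trigger would add to this. Power under the planned effect is unchanged with the harm bound and about 0.4 points lower (80.5% to 80.1%) with a Z ≤ 0 futility stop. That stop would also end about 55% of trials with equal arms, which is what a futility rule is for. Neither rule inflates type I error for benefit, since each acts only when HFNC looks no better.

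### The primary result is planned as percentages and an unstratified test, with no effect estimate or confidence interval and no use of the STOP-BANG randomization strata

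*Combined protocol and SAP*

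**What the plan says.** Section 14 (Biostatistics) states the target as an effect size: "The study is powered to detect a 50% reduction in the frequency of desaturation episodes in patients with HFNC". The control rate comes from a cited observational study, which the plan says "reported a 51% incidence rate for desaturation episodes below 90% in patients with standard nasal cannula". The sample size, 59 per group, follows from "Thus to detect a difference of 25% with 80% power and a type 1 error rate of 0.05".

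For reporting, the same section says that "categorical data will be summarized using frequencies and percentages" and gives the primary comparison as: "The proportions of desaturation episodes below 90% in the two groups will be compared using a Z test or Fisher's exact test". No section names a risk difference or ratio, a confidence interval, or a stratified analysis.

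Section 3 (Concise Summary of Project) stratifies subjects by STOP-BANG score, 5 or more against 4 or fewer, and randomizes within those strata. Section 14 does not mention them.

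Section 14 also plans one interim analysis at half of enrolment, with O'Brien-Fleming alpha spending and the possibility of "early termination for effectiveness if the observed difference at the time is large enough".

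**The concern.** The trial is designed around the size of a reduction, but the planned output answers only whether the arms differ. With 59 per arm, a moderate observed difference can easily fail to reach significance while still being compatible with the full planned benefit. Reported as two percentages and a p-value, such a result invites the conclusion that high-flow oxygen does not help, which the data could not support.

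The strata are a second, smaller gap. STOP-BANG was presumably chosen because sleep apnea risk is expected to predict desaturation. An analysis that ignores a prognostic stratification factor usually stays valid but is somewhat conservative, and it sets aside information the trial has already collected.

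**Working it through.** **Inputs (Section 14):** control rate 51%; difference 25 points, so 26% on HFNC; type I error 0.05, taken as two-sided because that reproduces the stated size; power 80%; 59 per group.

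**1. The plan's own figure.** Pooled-variance formula, average rate (0.51 + 0.26)/2 = 0.385:

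n = [1.96 × √(2 × 0.385 × 0.615) + 0.842 × √(0.51 × 0.49 + 0.26 × 0.74)]² / 0.25²
= [1.349 + 0.560]² / 0.0625 ≈ 58.3, so **59 per group**. The stated size reproduces.

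**2. Precision at the final analysis.** 95% half-width = 1.96 × √(0.51 × 0.49/59 + 0.26 × 0.74/59) = 1.96 × 0.0866 = 0.170, or **about 17 points**. Using the final critical value after one O'Brien-Fleming-type look (1.969) instead of 1.96 leaves it at 17.

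**3. A non-significant example, 45% v 35% with 59 per arm.**
- Test: z = 0.10 / √(2 × 0.40 × 0.60/59) = 0.10 / 0.0902 = 1.11, two-sided p ≈ 0.27.
- Interval: 0.10 ± 1.96 × √((0.45 × 0.55 + 0.35 × 0.65)/59) = 0.10 ± 0.176, or **about -8 to +28 points**.

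The interval contains both 0 and the planned 25. The p-value does not show this.

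**4. Strata.** The documents give no desaturation rates by STOP-BANG stratum, so the precision gained by stratifying cannot be calculated. The half-widths above are unstratified approximations.

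**5. What an early efficacy stop does to the raw difference.** The documents give no numerical boundary. The Lan-DeMets O'Brien-Fleming bound at half the information, two-sided 0.05, is |Z| ≥ 2.963. Exact binomial enumeration with true rates 51% v 26% and a pooled Z test gives:

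| Evaluable per arm at interim | Chance of stopping | Mean raw difference if stopped |
|---|---|---|
| 29 | 14.4% | 44.1 points |
| 30 | 15.9% | 43.2 points |
| 33 | 19.8% | 41.1 points |

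Across the choices the plan leaves open (spending or classical boundary of 2.797; pooled Z, unpooled Z or Fisher; enrolled or evaluable patients), the conditional mean runs from about 39 to 46 points and the chance of stopping from about 11% to 29%.

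At 29 per arm, trials that continue average 23.4 points. Over all trials the mean is 0.144 × 44.1 + 0.856 × 23.4 = 26.4 points, a bias of about 1.4. Simulations over two boundaries and several interim sizes put it between 1.4 and 1.8.

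**6. Would a stage-wise adjustment change the estimate after such a stop?** There is only one interim look. Under stage-wise ordering, a first-look stop is ranked only against first-look results at least as extreme, so the median-unbiased estimate equals the raw one. For an observed 44 points at 29 per arm, SE = √(2 × 0.385 × 0.615/29) = 0.128. Both the stage-wise and the ordinary 95% interval are 19 to 69 points, and p = 0.00057 either way.

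**7. A repeated confidence interval does change.** Take an observed 44 points at 30 per arm, centred on the planned average rate (60.5% v 16.5%): SE = √((0.605 × 0.395 + 0.165 × 0.835)/30) = 0.112. The ordinary interval is 0.44 ± 1.96 × 0.112, about 22 to 66 points. The repeated interval is 0.44 ± 2.963 × 0.112, about 11 to 77 points.

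**The case against.** The strongest reply is that an interval can be worked out by anyone from the counts and percentages already planned, so leaving it out of Section 14 loses nothing. That is true of an unstratified interval. It is not true of a stratified one unless counts by stratum are published, and it does not commit the report to reading a non-significant result from the interval. It is also fair to say that an unstratified test after stratified randomization is not invalid, and that its cost here cannot be sized.

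A reader might go further and infer that the plan yields a wrong effect size, because a stop for efficacy would report about 44 points when the truth is 25, and that a median-unbiased, stage-wise estimate is needed. The documents do not support that reading:
- The 44 is an average only among trials that stop, about 14% to 20% of them under the design effect with the spending boundary and pooled Z. In trials that continue, the raw difference is slightly low, and the overall bias is under 2 points.
- Overestimation after an efficacy stop is common to group-sequential trials. The planned alpha spending controls type I error and makes an early stop uncommon, and the raw percentages still describe the data correctly.
- With a single interim look, the stage-wise method returns the raw estimate, the ordinary interval and the ordinary p-value (step 6), so it would correct nothing.

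**Conclusion.** The point holds as a reporting gap that is free to close. Section 14 provides no effect estimate or interval for the primary endpoint and leaves out the randomization strata. At 59 per arm the difference is known only to within about 17 points either way, so a non-significant p-value cannot separate no useful effect from too little information. This assumes the design rates, 59 evaluable patients per arm, and that the outcome is counted per patient, as the sample size calculation implies.

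Early-stop bias is a minor addition and not the main reason to change the plan. It is conditional on an infrequent event, its size depends on choices the plan leaves open, and it justifies at most a sentence on reporting. Neither the sample size nor the validity of the planned test is called into question.

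**What to change.** Add to Section 14, in substance:

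- The primary result is the difference between arms in the proportion of patients with at least one SpO2 reading below 90%, with a two-sided 95% confidence interval, estimated by Mantel-Haenszel over the STOP-BANG strata (5 or more v 4 or fewer). A matching stratified test would keep the p-value and interval consistent.
- A non-significant final result will be interpreted from this interval.
- Optional: if the trial stops early for efficacy, the report will say that the raw difference tends to overstate the effect, and will show a repeated confidence interval at the O'Brien-Fleming boundary beside it.

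The cost is a few lines of text and standard software. No extra patients or data are needed, since the strata are already collected, and the sample size is unchanged. The only downside is in the optional part: after an early stop the repeated interval is visibly wider than the ordinary one (about 11 to 77 against 22 to 66 points in the example).
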